6.1.2.3. Premedication for other futuximab/modotuximab-related toxicities

If following the first dose, a participant experiences symptoms suggestive of other mild-to-moderate futuximab/modotuximab-related reactions (e.g., diarrhoea,), the participant may be premedicated with standard therapies to reduce the potential for such reactions in the future.

Based on ongoing review of participant safety data, the sponsor (or DMC) may implement additional mandatory premedication for all participants treated in this study should a pattern emerge of other mild-to-moderate futuximab/modotuximab-related reactions (e.g., IRRs and/or any other trends in futuximab/modotuximab-related toxicities) that are amenable to prophylaxis with standard agents. Such action will occur following discussions between the investigator(s) and the sponsor.

Any medications administered for either prophylaxis or therapy of signs/symptoms related to futuximab/modotuximab will be documented on the appropriate page of the participant's e-CRF.

6.1.3. Administration of trifluridine/tipiracil

6.1.3.1. Dose/Route

- 35 mg/m²/dose, orally; maximum of 80 mg per dose based on the trifluridine component.

6.1.3.2. Schedule

- Trifluridine/tipiracil should be administered before futuximab/modotuximab administration.
- Trifluridine/tipiracil should only be given on Days 1 through 5 and Days 8 through 12 of each cycle. If doses are missed or held on those days, the participant should not make up for missed doses. Extension of study treatment into Days 6 to 7 or into the rest period (Days 13 through 28) is not permitted.
- Trifluridine/tipiracil should be taken with a glass of water within 1 hour after completion of morning and evening meals (or in accordance with the local SmPC of trifluridine/tipiracil).
- Any missed doses reported by the participant should be recorded in the e-CRF.
- Trifluridine/tipiracil dosage is calculated according to BSA (Body Surface Area). Table (6.1.3.2) 1 shows the number of tablets that are needed per calculated BSA for a dose of 35 mg/m². Table (6.1.3.2) 2 shows the number of tablets that are needed per calculated BSA for a reduced dose (30 mg/m², 25 mg/m² and 20 mg/m²). The BSA will be calculated by the site (in Safety Lead-In part) or IWRS (in Randomised part) using the following DuBois formula³⁰ all BSA calculations are rounded to 2 decimal places): BSA (m²) = ([Body Weight (kg)]^{0.425} x [Height (cm)]^{0.725}) x 0.007184.
- If at the beginning of the new treatment cycle, a participant's body weight decreases by $\geq 10\%$ from baseline, the site (in Safety Lead-In part) or IWRS (in Randomised part), will recalculate the participant's BSA and adjust trifluridine/tipiracil dosage.
- In case of change of dose level in Randomised part, the IWRS will provide the study site with the adjusted trifluridine/tipiracil dosage.
- No increase in trifluridine/tipiracil dose due to increase in BSA is permitted.

Table (6.1.3.2) 1 - Number of tablets of trifluridine/tipiracil per dose (standard dose) according to body surface area

Trifluridine/tipiracil Dose (2 x daily)	BSA (m ²)	Dosage in mg (2x daily)	Total daily dose (mg)	Tablets per dose (2x daily)	
				15 mg/6.14 mg	20 mg/8.19 mg
35 mg/m ²	< 1.07	35	70	1	1
	1.07 - 1.22	40	80	0	2
	1.23 - 1.37	45	90	3	0
	1.38 - 1.52	50	100	2	1
	1.53 - 1.68	55	110	1	2
	1.69 - 1.83	60	120	0	3
	1.84 - 1.98	65	130	3	1
	1.99 - 2.14	70	140	2	2
	2.15 - 2.29	75	150	1	3
	≥ 2.30	80	160	0	4

BSA = body surface area (calculate to 2 decimal places)

Table (6.1.3.2) 2 - Number of tablets of trifluridine/tipiracil per dose (reduced dose) according to body surface area

Trifluridine/tipiracil Dose (2 x daily)	BSA (m ²)	Dosage in mg (2x daily)	Total daily dose (mg)	Tablets per dose (2x daily)	
				15 mg/6.14 mg	20 mg/8.19 mg
Level 1 Dose reduction: From 35 mg/m ² to 30 mg/m ²					
30 mg/m ²	< 1.09	30	60	2	0
	1.09 - 1.24	35	70	1	1
	1.25 - 1.39	40	80	0	2

Trifluridine/tipiracil Dose (2 x daily)	BSA (m ²)	Dosage in mg (2x daily)	Total daily dose (mg)	Tablets per dose (2x daily)	
				15 mg/6.14 mg	20 mg/8.19 mg
	1.40 - 1.54	45	90	3	0
	1.55 - 1.69	50	100	2	1
	1.70 - 1.94	55	110	1	2
	1.95 - 2.09	60	120	0	3
	2.10 - 2.28	65	130	3	1
	≥ 2.29	70	140	2	2
Level 2 Dose Reduction: From 30 mg/m ² to 25 mg/m ²					
25 mg/m ²	< 1.10	25 ^a	50 ^a	2 (PM) ^a	1 (AM) ^a
	1.10 - 1.29	30	60	2	0
	1.30 - 1.49	35	70	1	1
	1.50 - 1.69	40	80	0	2
	1.70 - 1.89	45	90	3	0
	1.90 - 2.09	50	100	2	1
	2.10 - 2.29	55	110	1	2
	≥ 2.30	60	120	0	3
Level 3 Dose Reduction: From 25 mg/m ² to 20 mg/m ²					
20 mg/m ²	< 1.14	20	40	0	1
	1.14 - 1.34	25 ^a	50 ^a	2 (PM) ^a	1 (AM) ^a
	1.35 - 1.59	30	60	2	0
	1.60 - 1.94	35	70	1	1
	1.95 - 2.09	40	80	0	2
	2.10 - 2.34	45	90	3	0
	≥ 2.35	50	100	2	1

^a At a total daily dose of 50 mg, participants should take 1 x 20 mg/8.19 mg tablet in the morning (AM) and 2 x 15 mg/6.14 mg tablets in the evening (PM). BSA = body surface area (calculate to 2 decimal places)

Note: could be done in accordance with the local SmPC

6.1.4. Premedication for trifluridine/tipiracil

Trifluridine/tipiracil is associated with a moderate emetic potential; anti-emetic therapy is recommended to prevent nausea and vomiting. For more details see [Section 8.12.1](#).

6.1.5. Retreatment criteria

These criteria are applicable after any dose delay and before the start of each cycle:

- ANC $\geq 1.5 \times 10^9/L$.
- Platelets $\geq 75 \times 10^9/L$.
- Ongoing AEs (IMP-related) should NOT meet study discontinuation criteria.
- Ongoing AEs (IMP-related) should have either ameliorated to \leq Grade 1 severity, returned to baseline status, or resolved, with the exceptions of Grade 2 clinical events that are being adequately controlled with best supportive care (e.g. nausea, vomiting, diarrhoea, fatigue, rash) and asymptomatic laboratory abnormalities that are considered clinically insignificant and uncomplicated or that are resolving spontaneously or with conventional medical interventions.
- Ongoing AEs which, in the opinion of the investigator, should make it advisable to delay the administration of treatments.

Note: Safety criteria to be met prior to the start of each cycle could be in accordance with the local SmPC of trifluridine/tipiracil.

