8.11. Management of treatment dose adaptations due to toxicities

For participants who have experienced a dosing modification, reasons for dose modifications or delays, the supportive measures taken, and the outcome will be documented in the participant's source documents and recorded in the e-CRF.

In the futuximab/modotuximab plus trifluridine/tipiracil arm doses of either futuximab/modotuximab, or trifluridine/tipiracil, or both drugs can be modified, depending on the toxicity observed.

General rules:

Before starting a new treatment cycle, toxicity must have resolved as specified in the [Sections 8.11.1](#) and [8.11.2](#) and the safety criteria to be met as specified in the [Section 6.1.5](#).

- If toxicity due to any of the IMPs does not resolve during the given cycle to Grade 1 or baseline, the start of the next cycle will be delayed for a maximum of 30 days for trifluridine/tipiracil and 21 days for futuximab/modotuximab (see [Sections 8.11.1](#) and [8.11.2](#)). If more than the maximum delay period is needed for recovery, the next cycle should be started with the IMP not concerned by the toxicity.
- If, in the opinion of the investigator, the toxicity is clearly related to one of the treatments, reduction of one and not the other agent is appropriate. If, in the opinion of the investigator, the toxicity is related to the futuximab/modotuximab only futuximab/modotuximab should be reduced according to recommended dose modifications. If, in the opinion of the investigator, the toxicity is related to the trifluridine/tipiracil only trifluridine/tipiracil should

be reduced according to recommended dose modifications. If the toxicity is related to the combination of two agents, both agents should be reduced (if applicable), interrupted or discontinued according to the recommended dose modifications.

- Participants may have trifluridine/tipiracil discontinued and continue on futuximab/modotuximab alone. Similarly, participants may discontinue futuximab/modotuximab and continue on trifluridine/tipiracil alone if appropriate.

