8.11.1. Management of treatment dose adaptations due to trifluridine/tipiracil toxicities

All toxicities related to trifluridine/tipiracil must have resolved to Grade 1 or baseline before the start of a new treatment cycle.

In the event of haematological and/or non-haematological toxicities, rules for trifluridine/tipiracil dose interruption and resumption are provided in [Table \(8.11.1\) 1](#); rules for dose modifications are provided in [Table \(8.11.1\) 2](#) and [Table \(8.11.1\) 3](#).

Treatment interruptions are regarded as lost treatment days and missed doses should not be replaced; the planned treatment schedule should be maintained.

A new treatment cycle with trifluridine/tipiracil can be started only if neutrophils count is $\geq 1.5 \times 10^9/L$ and platelets count is $\geq 75 \times 10^9/L$.

Table (8.11.1) 1 - Dose interruption and resumption criteria for haematological toxicities related to myelosuppression

Parameter	Interruption criteria*	Resumption criteria**
Neutrophils	$< 0.5 \times 10^9/L$	$\geq 1.5 \times 10^9/L$
Platelets	$< 50 \times 10^9/L$	$\geq 75 \times 10^9/L$

* Interruption criteria apply only during active treatment intake period (i.e., D1-5 and D8-12) based on an unscheduled laboratory assessment.

**Resumption criteria apply to the start of the next cycle for all participants regardless of whether or not the interruption criteria were met.

Table (8.11.1) 2 - Recommended dose modifications in case of haematological adverse event related to myelosuppression

Adverse event related to myelosuppression	Recommended dose modifications
Febrile neutropenia NCI-CTCAE Grade 4 neutropenia count $< 0.5 \times 10^9/L$ that results in more than 1 week's delay in start of next cycle	Don't start a new treatment cycle until the resumption criteria are met (Table (8.11.1) 1) When resuming dosing, decrease the dose level by 5 mg/m ² from the previous dose level (Table (6.1.3.2) 2)
NCI-CTCAE Grade 4 thrombocytopenia $< 25 \times 10^9/L$ that results in more than 1 week's delay in start of next cycle	Dose reductions are permitted to a minimum dose of 20 mg/m ² /dose twice daily Do not increase dose after it has been reduced

Table (8.11.1) 3 - Recommended dose modifications in case of non-haematological adverse event related to trifluridine/tipiracil

Adverse event related to trifluridine/tipiracil	Recommended dose modifications

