NCI-CTCAE non-haematologic grade 3 or 4 adverse reaction; except for grade 3 nausea and/or vomiting controlled by antiemetic therapy or diarrhoea responsive to antidiarrheal medicinal products.	Don't start a new treatment cycle until toxicity resolves to Grade 1 or baseline When resuming dosing, decrease the dose level by 5 mg/m ² from the previous dose level (Table (6.1.3.2) 2) Dose reductions are permitted to a minimum dose of 20 mg/m ² /dose twice daily Do not increase dose after it has been reduced

If the participant recovers from toxicities requiring treatment interruption:

- During the 2-week active treatment intake period of a cycle (treatment D1-D12):
 - If no dose reduction is required, trifluridine/tipiracil may be resumed during that cycle. Missed doses must not be caught up.
 - If a dose reduction is required, trifluridine/tipiracil should be resumed at the start of the next treatment cycle at the appropriate dose level.
- During the rest period (D13-28):
 - Start the next cycle on schedule at the appropriate trifluridine/tipiracil dose level.

If the toxicity does not resolve during the given cycle to Grade 1 or baseline, the start of the next cycle may be delayed by a maximum of 30 days from the last dose of trifluridine/tipiracil administered to allow the initiation of both IMPs at the same time in the next cycle. If more than 30 days from the last dose administered are needed for recovery, the next cycle should be started by omitting trifluridine/tipiracil doses as needed (i.e. next cycle is started with only S95026 and trifluridine/tipiracil is reintroduced later) or the participant may have trifluridine/tipiracil discontinued, according to investigator's judgement.

Note: Interruption/resumption criteria and recommended dose modifications of trifluridine/tipiracil could be done in accordance with the local SmPC (Summary of Product Characteristics)).

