8.11.2.2. Dose Delay

Toxicities may be managed by delay in dosing, provided they do not meet the criteria for IMP discontinuation ([Section 5.8.1](#)). In such cases, the period between any 2 scheduled doses may be extended up to 3 days (inclusive) to allow an improvement of the toxicity. Such delays will be considered an extension within the current cycle. If a delay of more than 3 days from the scheduled dose date is necessary, the dose should be omitted and proceed to the next scheduled dose (i.e. 14 days from the last dose).

If 3 consecutive doses are needed to be omitted (i.e. more than 21 days from the last dose of futuximab/modotuximab), the participant should be discontinued from futuximab/modotuximab. All delays of futuximab/modotuximab must be documented on the appropriate page of the participant's e-CRF.

If toxicity does not resolve during the given cycle to Grade 1 or baseline, the start of the next cycle may be delayed by a maximum of 21 days from the last dose of futuximab/modotuximab administered to allow the initiation of both IMPs at the same time in the next cycle. If more than 21 days from the last dose administered are needed for recovery, futuximab/modotuximab should be discontinued and the next cycle will start with only trifluridine/tipiracil.

Dosing may be restarted at the same dose, as clinically indicated. However, administration of futuximab/modotuximab may only be restarted provided retreatment criteria are met ([Section 6.1.5](#)).

For treatment restart with no dose reduction:

- If treatment restart after the omission of 1 dose (i.e. treatment delay up to 14 days from the last dose), it is recommended that dosing restart with maintenance dose of 6 mg/kg;
- If treatment restart after the omission of 2 consecutive doses (i.e. treatment delay up to 21 days from the last dose), it is recommended that dosing re-start with the re-administration of a loading dose of 9 mg/kg followed by weekly maintenance doses of 6 mg/kg.

For treatment restart with dose reduction, see Section 8.11.2.3.

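### Protocol 6.1.5 requires blood count recovery before any cycle or restart, but 8.11 and 8.11.1 direct a futuximab/modotuximab-only cycle in a case where counts may still be low, and no exemption is stated

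*Protocol*

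**What the plan says.** Four places in the protocol bear on this.

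- **6.1.5 (Retreatment criteria).** "These criteria are applicable after any dose delay and before the start of each cycle". The list starts with neutrophils of at least 1.5 × 10^9/L and platelets of at least 75 × 10^9/L. The lead-in names no drug. A note adds: "Safety criteria to be met prior to the start of each cycle could be in accordance with the local SmPC of trifluridine/tipiracil".
- **8.11 (general rules).** Before a new cycle, toxicity must have resolved and the 6.1.5 criteria must be met. The first bullet then deals with toxicity that does not resolve: past the maximum delay, "the next cycle should be started with the IMP not concerned by the toxicity".
- **8.11.1 (trifluridine/tipiracil toxicities).** The count rule is worded for one kind of cycle: "A new treatment cycle with trifluridine/tipiracil can be started only if neutrophils count is" at the threshold, with a matching platelet condition. If recovery takes more than 30 days from the last trifluridine/tipiracil dose, "the next cycle should be started by omitting trifluridine/tipiracil doses as needed", which the text explains as a cycle of S95026 (futuximab/modotuximab) only. The stated alternative is to discontinue trifluridine/tipiracil, at the investigator's judgement.
- **8.11.2.2 (antibody dose delay).** After a delay, "administration of futuximab/modotuximab may only be restarted provided retreatment criteria are met", with a reference back to 6.1.5. The same section has the stopping rule: "If 3 consecutive doses are needed to be omitted", meaning more than 21 days since the last infusion, the participant comes off the antibody.

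**The concern.** Take a participant on the combination whose neutrophils or platelets are still below threshold more than 30 days after the last trifluridine/tipiracil dose. Section 8.11.1 directs a cycle of antibody alone. Section 6.1.5, cited again in 8.11 and 8.11.2.2, says no cycle and no restart until the counts recover. A site can follow either text and be within the protocol.

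One site would infuse the antibody with counts below the stated minimum. Another would withhold it and might then apply the 21-day rule, ending antibody treatment because of a toxicity of the other drug. At stake are participant safety and the meaning of what the SAP reports: missed infusions and relative dose intensity for the antibody (SAP 3.3.1.2), and adverse events leading to withdrawal of each drug (SAP 3.5.1).

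**Working it through.** The plan gives no figure to reproduce, and no sample size, power or alpha depends on this point. The check compares texts and counts days.

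**Step 1: is the trigger for the antibody-only cycle the same state that fails 6.1.5?**

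| Count | Not resolved to Grade 1 (SAP Table (7.3) 2) | Required at entry (Protocol 5.3.1, criterion 16a) | Required by 6.1.5 |
|---|---|---|---|
| Neutrophils, × 10^9/L | below 1.5 | at least 1.5 | at least 1.5 |
| Platelets, × 10^9/L | below 75 | at least 100 | at least 75 |

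The 8.11.1 trigger is toxicity not back to Grade 1 or baseline. Baseline could not be below the 6.1.5 minimum for either count, so the baseline option gives no way round it. For these two toxicities, being eligible for the antibody-only cycle means failing 6.1.5. The 6.1.5 tolerance for insignificant laboratory abnormalities belongs to its adverse event item, not to the separate neutrophil and platelet items.

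**Step 2: when do the two rules meet?** The inputs are the last planned trifluridine/tipiracil dose on Day 12 (Protocol 6.1.3.2), the last planned antibody dose on Day 22 (6.1.1.3), 30 days from the last dose for the first (8.11.1) and 21 days for the second (8.11.2.2).

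- Trifluridine/tipiracil: 12 + 30 = 42, so the antibody-only cycle is directed from Day 43.
- Antibody: 22 + 21 = 43, so Day 43 is the last day within its limit. The infusions due on Days 29 and 36 have been omitted, and omitting Day 43 would be the third in a row.

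On schedule, the two rules share a single day.

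**Step 3: does this depend on the schedule?**

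| Last trifluridine/tipiracil | Antibody-only cycle from | Last antibody | Antibody limit | Days shared |
|---|---|---|---|---|
| D12 | D43 | D22 | D43 | 1 |
| D8 | D39 | D22 | D43 | 5 |
| D5 | D36 | D22 | D43 | 8 |
| D12 | D43 | D15 | D36 | none |

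The ±2-day infusion window also matters. With trifluridine/tipiracil to Day 12, an infusion on Day 20 gives 20 + 21 = 41, so no day is shared. One on Day 24 gives 24 + 21 = 45, so three days are shared (D43 to D45). In the cases with no shared day, the antibody limit passes before 8.11.1 reaches its antibody-only instruction.

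**Step 4: is there an exemption?** No section says that an antibody-only cycle is free of the 6.1.5 counts, or which section prevails.

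**The case against.** The best reply is that the 8.11 bullet is itself the exception. It opens with toxicity that has not resolved, so it governs the case in which the opening requirement has failed. If the opening sentence overrode it, the bullet would have no effect for any unresolved cytopenia. Section 8.11.1 repeats the instruction and ties its count rule to cycles that contain trifluridine/tipiracil. This is a plausible reading and may be what was intended. However, it is nowhere stated, and 8.11.2.2 points the other way by restating 6.1.5 within the antibody's own section.

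Other parts of the case against stand and limit the point:

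- A reader might infer that low counts permanently end the antibody. The documents do not settle that. The 21-day rule sits in 8.11.2, which is headed for antibody toxicities. Its three-dose wording is not limited by cause, but applying it to a hold caused only by trifluridine/tipiracil is one reading among others.
- A reader might infer that every antibody-only cycle breaches 6.1.5. It does not: the over-30-day rule also covers non-haematological toxicity, where counts may be normal.
- A reader might infer from the quoted neutropenia rates that long delays will be common. Grade 3 or higher neutropenia is given as 34% on trifluridine/tipiracil alone (2.8), and as 55% with cetuximab and 10.9% with panitumumab (both 2.3.2). These are incidences with no duration attached, and 8.12.3 permits growth factor support.
- The 6.1.5 note may change the cycle-start criteria at some sites. The content of the local labels is not in the documents, and the note does not exempt the antibody.

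**Conclusion.** The inconsistency is real and limited. For neutropenia or thrombocytopenia lasting more than 30 days after the last trifluridine/tipiracil dose, 8.11 and 8.11.1 direct what 6.1.5 and 8.11.2.2, read as written, forbid. Undelayed infusions within a cycle are not affected, because 6.1.5 applies only at cycle start and after a delay.

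In time, the overlap is one day (D43) with all doses on schedule, and between none and eight days in the schedules checked. This assumes that both limits run from the last dose of each drug, as 8.11.1 and 8.11.2.2 state. The number of participants affected cannot be estimated, because the share with counts still low at that point is not given.

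A reader might expect an effect on discontinuation rates in the experimental arm of the randomised comparison. The SAP introduction rules that out: the randomised part was cancelled when the study was discontinued during the Safety Lead-In, for strategic reasons. What remains is the single-arm Lead-In, planned at about 25 participants, including anyone still on treatment and the interpretation of its exposure data, plus any reuse of the protocol. The point deserves correction because it concerns dosing with low counts. It does not touch any efficacy conclusion.

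**What to change.** Reconcile 6.1.5, 8.11, 8.11.1 and 8.11.2.2 so that one statement, cross-referenced from the others, says:

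1. whether the neutrophil and platelet criteria apply to a cycle or restart of futuximab/modotuximab alone;
2. whether the 21-day limit applies while those criteria are unmet because of trifluridine/tipiracil, and if so how.

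Which clinical rule is right is for the sponsor and its medical advisers, and none is proposed here. The cost is wording in one amendment, with no added visits, samples or analyses. If the protocol will not be amended again, the study report could state which reading sites followed wherever a Lead-In participant met this situation.

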6.2. IMP and NIMPs dispensing

IMPs (futuximab/modotuximab and trifluridine/tipiracil) will be dispensed by the pharmacist/responsible of the healthcare establishment upon prescription of the investigator only.

The investigator may only use the IMPs provided for the participants involved in the study and treated under his/her responsibility. Further instructions for the preparation and dispensation of futuximab/modotuximab are described in the Pharmacy Manual.

All dosages of IMPs prescribed to the participant and all dose changes during the study must be recorded in the e-CRF. The exact dates and times at which futuximab/modotuximab was administered by the investigator and trifluridine/tipiracil was taken by the participant must be reported in the e-CRF.

The detachable portion of the label on the IMP box must be stuck by the responsible of the healthcare establishment on an IMP label collection form or on the prescription form where the IMPs are dispensed by a pharmacist.

NIMPs will be dispensed in accordance with [Section 6.1.2](#).

For the Randomised part the treatment arm will be allocated via IWRS using a central randomisation (1:1) to trifluridine/tipiracil in combination with futuximab/modotuximab or trifluridine/tipiracil monotherapy with stratification by ECOG PS (0 *versus* 1), ECD EGFR mutation (presence *versus* absence) and previous regimens of treatment (2 *versus* ≥ 3). A connection to the IWRS should be performed at each concerned visit to know the allocated kit number(s) to be dispensed to the participant (please see details in IWRS manual).

